6.4 STUDY INTERVENTION COMPLIANCE

The injected dose is documented in CRIS.

6.5 CONCOMITANT THERAPY

This study has no concomitant therapies.

Abbreviated Title: [¹⁸F]SF12051 in Healthy Subjects

Version Date: 12/05/23

7 STUDY INTERVENTION DISCONTINUATION AND PARTICIPANT DISCONTINUATION/WITHDRAWAL

7.1 DISCONTINUATION OF STUDY INTERVENTION

Discontinuation instituted by the investigator has been rare in our PET studies but would likely occur during one of the scans (i.e., MRI, two PETs). Examples include a participant experiencing such anxiety that the investigator recommends study discontinuation, even though the participant is willing to proceed, or a post-scan safety measurement that indicates a clinically significant abnormality that must be investigated and rectified before they can proceed.

Participants are free to withdraw from participation in the study at any time upon request.

An investigator may discontinue or withdraw a participant from the study for the following reasons:

- A clinically significant AE, laboratory abnormality, or other medical condition or situation suggesting that continued participation in the study would not be in the best interest of the participant.
- Screen failure, including positive pregnancy test.
- Investigator discretion – e.g., excessive anxiety of the participant.

Any new clinically relevant finding will be reported as an AE, and the cause of discontinuation will be recorded in CRIS. In the event of any discontinuation, we will seek to obtain the next safety measure – i.e., post-scan safety labs or EKG.

7.2 PARTICIPANT DISCONTINUATION/WITHDRAWAL FROM THE STUDY

Participants are free to withdraw from participation in the study at any time upon request.

An investigator may discontinue or withdraw a participant from the study for the following reasons:

- Significant study intervention non-compliance
- If the participant meets an exclusion criterion (either newly developed or not previously recognized) that precludes further study participation
- Subject has completed the study follow-up period
- Death
- Screen Failure

7.3 LOST TO FOLLOW-UP

A participant will be considered lost to follow-up if they fail to return for a scheduled visit and is unable to be contacted by the study site staff.

The following actions must be taken if a participant fails to return to the clinic for a required study visit:

- The site will attempt to contact the participant and reschedule the missed visit as soon as practicable and counsel the participant on the importance of maintaining the assigned visit schedule and ascertain if the participant wishes to and/or should continue in the study.

- Before a participant is deemed lost to follow-up, the investigator or designee will make every effort to regain contact with the participant (where possible, three telephone calls and, if necessary, a certified letter to the participant's last known mailing address or local equivalent methods). These contact attempts should be documented in the participant's medical record or study file.
- Should the participant continue to be unreachable, they will be considered to have withdrawn from the study with a primary reason of lost to follow-up.

8 STUDY ASSESSMENTS AND PROCEDURES

8.1 SCREENING PROCEDURES

8.1.1 Screening activities performed prior to obtaining performed consent

Minimal risk activities that may be performed before the subject has signed a consent include the following:

- Email, written, in person, or telephone communications with prospective subjects
- Review of existing medical records to include H&P, laboratory studies, etc.
- Review of existing MRI, x-ray, or CT images

8.1.2 Screening activities performed after a consent for screening has been signed

Prior to consenting to this study, participants will have undergone an initial blood sample to determine TSPO genotype under protocol 01M0254 "The Evaluation of Participants with Mood and Anxiety Disorders and Healthy Volunteers", which allows for the sharing of collected data.

With the first visit under this protocol, all subjects will have a physical exam, EKG, and blood labs: CBC; acute care panel (Na, K, Cl, CO₂, creatinine, glucose, urea nitrogen); hepatic panel (alkaline phosphatase, ALT, AST, bilirubin total, and bilirubin direct); mineral panel (albumin, calcium, magnesium, phosphorus); prothrombin and partial prothrombin tests. Screening results will be reviewed by a clinically credentialed investigator before the subject undergoes any specific study procedures. Results of these tests will identify participants who should be excluded because of active medical problems or make participation in the protocol unsafe.

Subjects who successfully screen and are found eligible will be asked about their availability for scheduling of the PET scan(s) appointment. Occasionally, we have a last-minute cancellation due to scheduling conflicts, COVID exposure, etc. Given the complexities of arranging for the PET scan slot and synthesis of the ligand, we will inquire whether candidates have flexibility in their schedules to allow them to participate with less than 72 hours' notice. We will maintain a list of those who agree to be available on short notice so that we may contact them if we have a scheduled subject that needs to cancel. In the event that we schedule a participant with a 72-hour notice, we will provide an additional payment of \$250 if they come in and complete the PET scan.

8.2 STUDY EVALUATIONS & PROCEDURES

In addition to the screening procedures described in Section 8.1, all participants will undergo:

- *Brain MRI* (phase 2 and 4 only) A brain MRI will be obtained for anatomic localization and will be performed on a 3 Tesla scanner located at the NIH Clinical

Abbreviated Title: [¹⁸F]SF12051 in Healthy Subjects

Version Date: 12/05/23

Center (Bethesda, Maryland). The MRI will take about one hour. Participants will undergo safety screening prior to the MRI to rule out contraindications such as cardiac pacemaker. If a suitable MRI is already available under another protocol or for clinical reasons, it will not be repeated if performed within one year.

- **Pregnancy Tests.** For women of childbearing potential, urine pregnancy testing will be done within the 24 hours prior to any MRI or PET scan. If the pregnancy test is positive, PET and MRI will not be done, and the participant will be removed from the protocol.

8.2.1 PET Procedures

Radioligand

[¹⁸F]SF12051 will be administered via an indwelling intravenous catheter over ~1 minute, within four hours after synthesis of the radioligand. The radioligand is stable during this period.

Insertion of the intravenous line

An intravenous line will be placed in the arm. The venous line will be used to inject the radioligand and will be removed at the end of the day. The IV line may be replaced if it fails to remain patent.

PET acquisition for brain and/or lung imaging

PET scans will be performed using a PET/CT or the HRRT. The choice of the scanner for a particular study will depend on scanner availability. Participants will be placed on the scanner bed with their head held firmly in place with a thermoplastic mask or a head holder fixed to the bed. A transmission scan will be performed before the PET scan to measure and correct for attenuation. Tracer infusions will be performed in the nuclear medicine department, while the subject is on the scanner bed.

After an intravenous bolus of about 5 mCi, arterial blood samples will be drawn from the arterial catheter during the PET scan. We will collect about 20-25 arterial samples. First, blood samples will be drawn every 15 seconds after injection for about 3 to 5 minutes, and then they will be collected every 5, 10, 15, or 30 minutes. The total amount of arterial blood will be about 100 mL. PET images of the brain will be acquired in three-dimensional mode with increased length of frame for a total of 120 minutes. The duration may be shortened on the basis of the results of time stability analysis.

At the end of the scans, the arterial and venous lines will be removed, and the subject will be instructed to void frequently to minimize radiation exposure.

PET acquisition for dosimetry

Whole body dosimetry scans will be performed with a PET/CT. The choice of the scanner for a particular study will depend on scanner availability. No arterial sampling will be done for dosimetry studies. Both a pre-injection transmission scan and a series of dynamic emission scans will be acquired. Each subject will be imaged in contiguous segments from the top of the head to a point below the gonads. To minimize extraneous motion, all subjects may wear a head-holding mask and will have their arms and abdomen wrapped with body-restraining sheets. This may add some additional discomfort. Venous samples up to 30 mL may be obtained

Abbreviated Title: [¹⁸F]SF12051 in Healthy Subjects

Version Date: 12/05/23

to measure [¹⁸F]SF12051 levels. Before injection of the radioligand, a transmission scan will be acquired for subsequent attenuation correction. Then, an initial set of dynamic emission scans will be acquired following the intravenous injection of [¹⁸F]SF12051. The acquisition of each cycle will begin with an emission scan at the first bed position (i.e., the head), and continue by moving the bed distally to the next body segment. Then, a second transmission scan, identical to the first, will be performed followed by a second set of dynamic emission scans.

Arterial Line Placement

For brain scans, a radial artery catheter will be inserted by the NIH Clinical Center Anesthesiology Department, after the presence of adequate ulnar collateral flow has been established. The skin at the site of the puncture will be anesthetized with 1% lidocaine. The catheter will be perfused (3 mL/h) with heparin solution (600 units/L) during the procedure. The amount of heparin infused will be much smaller than the amount necessary to produce any systemic anticoagulant effect.

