1.1 SYNOPSIS

| | |
|---|---|
| Title: | Assessment of [¹⁸ F]SF12051 for Imaging the 18-kDa Translocator Protein (TSPO) in Brain and Whole Body of Healthy Subjects |
| Study Description: | This study is intended to provide information on the novel [¹⁸ F]SF12051 radioligand and its ability to localize and measure TSPO in the brain and body of healthy individuals. |
| Objectives: | 
Primary Objective: To study the brain uptake of [¹⁸F]SF12051 and perform kinetic modeling of the [¹⁸F]SF12051 in the three different TSPO genotypes.
 
Secondary Objectives: To study the brain retest characteristics, biodistribution and dosimetry of [¹⁸F]SF12051 in healthy subjects.
 |
| Endpoints: | 
Primary Endpoint: The distribution volume of the radioligand and stability over time calculated with compartmental modeling, attention paid to differences in mean distribution volumes between TSPO genotypes for determining genotype sensitivity.
 
Secondary Endpoints: Retest variability and reliability and organ-time-activity curves to determine biodistribution and dosimetry.
 |
| Study Population: | Up to forty-five (45) healthy male and female volunteers (18 years and older) of the three different TSPO genotypes for brain and whole-body imaging. |
| Phase: | N/A |
| Description of Sites/Facilities | Screening and PET imaging will be performed at the NIH Clinical Center. |
| Enrolling Participants: | |
| Description of Study Intervention: | Arterial line, PET scan, and brain MRI scan for absolute quantification of TSPO. Blood drawn from all subjects to determine TSPO genotype. |
| Study Duration: | 3 years |
| Participant Duration: | 1-4 visits, 2-6 hours per visit. |

Abbreviated Title: [¹⁸F]SF12051 in Healthy Subjects

Version Date: 12/05/23

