2.3.1.2 Radiation Exposure

Radiation exposure in this protocol will be from $[^{18}\text{F}]\text{SF12051}$ and the associated transmission scans. With our PET/CT scan, the effective doses for one head and one whole-body transmission scans 0.02 and 0.6 rem respectively. In addition, we routinely include the dose from two transmission scans in the event that it must be repeated in a subject. The effective dose from two head CT scans is 0.04 rem (and from four CT scans in case of test-retest acquisition is 0.08 rem) and from two whole body scans is 1.2 rem. The radiation exposure from $[^{18}\text{F}]\text{SF12051}$ is unknown, but ^{18}F -labeled compounds generally show very similar dosimetric values of about 20 $\mu\text{Sv}/\text{MBq}$ (0.074 rem/mCi) ([10](#)) or about 0.37 rem for a 5 mCi injection.

Please note that no pharmacological effects are expected from $[^{18}\text{F}]\text{SF12051}$. Therefore, only radiation risks are relevant to this tracer.

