9 STATISTICAL CONSIDERATIONS

9.1 STATISTICAL HYPOTHESIS

Primary Endpoint(s): We hypothesize that [¹⁸F]SF12051 will show strong binding affinity for TSPO regardless of genotype.

Secondary Endpoint(s): We hypothesize that the retest variability and reliability of [¹⁸F]SF12051 will allow its use in clinical protocols.

We hypothesize that the dosimetry and biodistribution of [¹⁸F]SF12051 will be similar to that of other ¹⁸F tracers.

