9.4.3 Analysis of the Secondary Endpoint(s)

The outcome measure for secondary endpoints will be the total distribution volume and the absorbed dose. Retest variability will be assessed as absolute variability and reliability will be assessed as interclass correlation coefficient (ICC). Dosimetry will be measured as absorbed dose and summarized as mean \pm SD for organs.

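### The plan lets scanner availability choose between two scanners for brain PET and does not keep a Phase 4 participant's test and retest scans on the same one (minor; cheap to fix).

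*Combined protocol and SAP*

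**What the plan says.** Section 8.2.1 covers brain acquisition. It states "PET scans will be performed using a PET/CT or the HRRT" and then "The choice of the scanner for a particular study will depend on scanner availability". It gives no other selection rule. Whole-body dosimetry scans, by contrast, are limited to PET/CT.

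Phase 4 is a test-retest brain study in up to 24 participants (section 1.2). Table 2 puts the two brain PET scans at visits 2 and 4, and the compensation table in section 5.6.2 puts them at visits 2 and 3. In both, they fall on separate visits.

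Section 9.4.3 defines the two retest outcomes: "Retest variability will be assessed as absolute variability and reliability will be assessed as interclass correlation coefficient (ICC"). It mentions no scanner term, stratum or exclusion. The hypothesis in section 9.1 is that variability and reliability "will allow its use in clinical protocols", with no numerical threshold.

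One other passage bears on equipment for the retest. Section 2.3.1.2 gives a transmission dose that "from four CT scans in case of test-retest acquisition is 0.08 rem".

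**The concern.** A test-retest study is meant to isolate the variation that comes from the tracer and its measurement under constant conditions. If a participant's two scans can be on different scanners, a difference between the machines adds to the difference between the scans.

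The outcome does not protect against this. V_T relates brain activity measured by the scanner to parent radioligand in arterial plasma, and the blood is counted separately on a gamma counter (section 8.2.2, Biospecimen Evaluations). A scanner-specific difference in measured brain activity would therefore pass into V_T and not cancel.

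At stake is a secondary objective. In a split pair, the offset is read as poor repeatability of [¹⁸F]SF12051. More pairs would not remove that contribution, and discarding split pairs at analysis loses scans that each needed an arterial line.

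**Working it through.** **What the documents supply.** There is no planned retest precision and no scanner offset, within-subject CV or split rate, so there is no figure of the plan's own to reproduce here. The only usable input is the between-subject spread in section 9.2: mean V_T 4.5 and SD 1.4 mL/cm³ in high-affinity binders with the earlier ligand, so 1.4/4.5 = 31.1%.

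**Assumptions (not in the documents).** Within-subject CV 7%, with 5% and 10% as alternatives; between-scanner V_T offset d of 5% or 10%; fraction f of pairs split of 10%, 25% or 50%; no systematic change from test to retest.

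**Ceiling on f.** If each scan independently goes to one scanner with probability p, then f = 2p(1−p). This is 37.5% at p = 0.25 and reaches its maximum of 50% at p = 0.5, or 12 of 24 pairs.

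**Absolute variability.** The SD of the test-retest difference is σ = √2 × 7% = 9.90%. The mean absolute difference with shift d is the folded-normal mean, σ√(2/π)·exp(−d²/2σ²) + d[1 − 2Φ(−d/σ)]:

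- d = 0: 7.899%
- d = 5%: 8.885%
- d = 10%: 11.618%

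The study-level value is (1−f) × 7.899 + f × (split-pair value):

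| Pairs split | d = 5% | d = 10% |
|---|---|---|
| 10% | 0.9×7.899 + 0.1×8.885 = 8.0% | 0.9×7.899 + 0.1×11.618 = 8.3% |
| 25% | 0.75×7.899 + 0.25×8.885 = 8.145, i.e. 8.1% | 0.75×7.899 + 0.25×11.618 = 8.8% |
| 50% | 0.5×7.899 + 0.5×8.885 = 8.4% | 0.5×7.899 + 0.5×11.618 = 9.8% |

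This treats d as a shift relative to the pair mean. If the offset multiplies one scan, 10% becomes 0.10/1.05 = 9.5% of the pair mean, so the 10% column is slightly high.

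**Other CVs, at the 50% ceiling.** With a 5% CV, 5.6% becomes 6.3–8.1%. With a 10% CV, 11.3% becomes 11.6–12.6%.

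**ICC.** Taking the 31.1% as total single-scan spread, ICC = (0.311² − 0.07²)/(0.311² + f·d²/2). With d = 0 this is 0.949. For d = 5% and 10% it is 0.948 and 0.944 at f = 10%, 0.946 and 0.937 at 25%, and 0.943 and 0.925 at 50%.

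**Comparison with sampling error.** The SD of the absolute difference is 9.90% × √(1 − 2/π) = 5.97%. The 95% half-width for its mean is t(0.975, n−1) × 5.97/√n:

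- n = 24: 2.5 points
- n = 16 (8 split pairs left out): 3.2 points
- n = 12 (12 left out): 3.8 points

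The largest rise in the 7% table is 9.8 − 7.9 = 1.9 points, below the 2.5-point half-width.

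**The case against.** The strongest reply is that the harm is assumed. No document gives an offset or says that any pair will be split, and with no offset nothing happens. That stands, and it is why the figures are offered only as a range.

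Second, the text can be read as pointing away from split pairs. The four head CT scans allowed for test-retest fit both scans being on PET/CT, and section 2.3.1.2 gives transmission doses for PET/CT only. The availability sentence also appears word for word under dosimetry, where only PET/CT is permitted, which suggests generic wording. The phrase about a particular study could mean one participant's imaging and not one session. These points make frequent splitting less plausible, but none is a rule: the CT figure is a dose allowance, and section 8.2.1 still permits the HRRT.

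Third, the effect is small, the endpoint is secondary, the study is described as exploratory and no threshold is set. With genotype groups analyzed separately (section 9.4.7) and about 24/3 = 8 retest pairs per group, the half-width is about 5.0 points. This also stands and keeps the point minor.

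Fourth, the direction is not guaranteed. If V_T shifts systematically between test and retest, an opposing scanner offset can lower absolute variability: at 7% CV, a −5% shift met by a +5% offset gives 7.9% in place of 8.9%.

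Finally, same-scanner pairing leaves scanner differences between participants. By the same formulas this nudges the ICC from 0.949 to 0.950–0.951. It also does nothing for V_T comparisons between genotypes, though a record of the scanner used would at least make those differences visible.

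**Conclusion.** The gap is real and minor. The plan states a rule, availability, that permits a test-retest pair to be split between two scanners, and nothing in the design or analysis prevents or handles that. Absent a systematic test-to-retest shift, an offset makes retest performance look worse. In the illustration, absolute variability rises by about 0.1 to 1.9 points from 7.9%, and the ICC drops by at most 0.024. All of this rests on an assumed CV, offset and split rate.

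Three stronger readings are tempting and not supported:

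- A reader might infer that about half the pairs will be split. That is the ceiling under independent assignment. The documents do not say that the scanners are equally available or that scans are assigned independently, and the CT allowance leans the other way.
- A reader might infer that the retest conclusion would be overturned. No threshold is stated against which that could be judged.
- A reader might see a companion flaw in the same section's sentence "The duration may be shortened on the basis of the results of time stability analysis", fearing that low-affinity binders' scans would be cut short on other genotypes' data. That wording is permissive and conditional on stability results. All genotypes are accepted from the start (section 9.2), and nothing says the decision would leave out low-affinity binders. It is a separate matter and no part of this conclusion.

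**What to change.** In section 8.2.1, require both Phase 4 scans of a participant to be acquired on the same scanner, and record the scanner used for every brain scan. If a split pair cannot be avoided, flag it. In section 9.4.3, report absolute variability and the ICC with and without split pairs.

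The cost is less freedom in scheduling the second scan, and possibly an occasional delayed or lost pair. Section 8.1.2 acknowledges the difficulty ("Given the complexities of arranging for the PET scan slot and synthesis of the ligand") and describes last-minute cancellations, so the cost is not zero. No participants or procedures are added. Preventing splits is preferable to removing split pairs afterwards, which would widen the half-width from 2.5 to 3.2 points if 8 of 24 pairs were left out, or to 3.8 if 12 were.

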8.2.2 Biospecimen Evaluations

After injections of the radioligand during brain scans, arterial sampling will be performed continuously at early time points and discretely at later time points, but this plan can be modified if required to improve quality of data. The arterial blood samples will be processed for total radioactivity through a gamma counter and will be processed through high performance liquid chromatography (HPLC) to measure metabolites. Correlation between arterial radioactivity and brain activity via the PET scan will allow for pharmacokinetic modeling and accurate quantification of the signal.

8.2.3 Correlative Studies for Research/Pharmacokinetic Studies

See Section **Error! Reference source not found.**

8.2.4 Samples for Genetic/Genomic Analysis

Blood for TSPO screening will be acquired only under protocol 01M0254.

8.2.4.1 Management of Results

Participants will have access to “clinical” medical results via the patient portal (e.g., laboratory tests, EKG, and MRI). In addition, we will notify them if any of these results are abnormal. They will not have access to investigational results from the PET scan, as they have no normal ranges.

8.2.4.2 Genetic counseling

None.

8.3 SAFETY AND OTHER ASSESSMENTS

Safety Monitoring of PET Scans

Data for safety monitoring will be recorded at three timepoints: no more than three hours before injection, about the middle of the PET scan, and after the PET scan. Recorded data include: blood pressure, pulse, respiratory rate, and EKG (either 3- or 12-lead). The following laboratory tests will also be obtained, but only at two timepoints (before and after the PET scan: CBC, acute care panel (Na, K, Cl, CO₂, creatinine, glucose, urea nitrogen), hepatic panel

Abbreviated Title: [¹⁸F]SF12051 in Healthy Subjects

Version Date: 12/05/23

(alkaline phosphatase, ALT, AST, bilirubin total, and bilirubin direct), mineral panel (albumin, calcium, magnesium, phosphorus).

Pregnancy Tests

For women of childbearing potential, urine pregnancy testing will be done within the 24 hours prior to any MRI or PET scan. If the pregnancy test is positive, PET and MRI will not be done, and the participant will be removed from the protocol.

Follow-up Procedures

Participants will be contacted one to three days after each PET scan to determine whether they have had any untoward sequelae.

